Title: Visual Restoration for Hemianopia

RSRB No.: RSRB00069879

Sponsor-Investigator: [name]. M.B.A.

Principal Investigator (Study Site 1): [name]. M.B.A.
Professor and Chair, Flaum Eye Institute
University of Rochester
[name]
Rochester, NY, 14642
USA

Daytime [contact]

Sub-Investigator 1 (Study Site 2): [name].
Robert Z. & Nancy J. Greene Professor of Ophthalmology
Bascom Palmer Eye Institute
University of Miami Health Services
[name]
Miami, Florida 33136
Daytime [contact]

Sub-investigator 2 (Study Site 3): [name]
Scheie Eye Institute
Department of Ophthalmology
University of Pennsylvania
Philadelphia, PA 19104
Daytime [contact]

Purpose: This project will collect data to quantify the effect of visual training on visual defects resulting from damage to the primary visual cortex. Subjects will be recruited, undergo baseline visual testing, undergo visual training designed to reduce their visual deficit, and perform post-training visual tests. This research is designed to determine if different visual training treatments are capable of reducing visual defects in a large population of adult subjects with cortical blindness in a double blind clinical trial.

Background and Motivation for the study: When brain damage is incurred in adulthood, through stroke, trauma, or other neurodegenerative conditions, functional deficits result depending on the brain region that was affected. As roughly half of the human cerebral cortex is devoted to visual processing, many people who suffer brain damage experience consequent impairments in vision. When damage affects the primary visual cortex (V1), the visual deficits are severe and are described as cortical blindness (CB), or hemianopia/quadrantanopia, depending on the size of the defect. CB dramatically impacts the lives of those affected, decreasing quality of life (Gall et al., 2008; Gall et al., 2009; Gall et al., 2010). CB subjects often lose the ability to drive (de Jong and Warmink, 2003; Papageorgiou et al., 2007), reducing their independence, while others who continue to drive pose a potential danger to themselves and others (Bowers et al., 2009, 2010; Bowers et al., 2014). Those suffering from CB also have other types of impaired daily functioning (Ramrattan et al., 2001), and reduced independence (Jongbloed, 1986).

Currently, there is no accepted treatment for cortical blindness. Some spontaneous recovery of vision was reported in a portion of subjects during the first 2-3 months following a stroke (Zhang et al., 2006). However, after this period the visual deficit is believed to become stable and permanent (Horton, 2005; Pollock et al., 2011). As such, in the rare instances when subjects are prescribed rehabilitation, it is essentially limited to substitution (Rossi et al., 1990; Peli, 2000) or compensation therapies (Weinberg et al., 1977; Kerkhoff, 1999, 2000; Spitzyna et al., 2007). In the limited number of subjects who benefit from these therapies, quality of life and daily functioning are improved (Weinberg et al., 1977; Spitzyna et al., 2007). However, neither therapy is able to restore any of the lost vision; instead, they are designed to teach subjects how to make use of what vision they have left more effectively (Lane et al., 2010).

In order to restore lost vision, subjects need to undergo restitution therapy. Multiple research studies have shown visual training to recover particular functions within chronic CB fields (See Melnick et al., 2016 for review). These studies have shown that in addition to improving performance on the trained tasks, such training can also recover untrained aspects of vision, such as those measured by standard, clinical visual perimetry (Cavanaugh and Huxlin, 2017). However, none of these studies were unbiased (i.e., subjects were not randomized and no blinding was used). To fill this important gap in the field, we have designed the present double blind clinical trial to assess whether visual restitution training using visual discrimination tasks presented in the blind field are clinically relevant and obtainable in a larger patient population. The trial will involve recruiting CB patients, measuring their baseline visual performance, randomizing them to one of two treatment groups, training them with one of two types of visual discrimination training therapy and bringing them back for a repeat of all baseline visual measurements. The results of this study will be submitted for publication to scientifically and clinically relevant journals, and they will be submitted to the Food and Drug Administration for approval.

Criteria for subject selection

1. Number of subjects: 20 subjects will be recruited at each of three study sites, leading to a total of 60 subjects. The subjects will be divided randomly into two training cohorts, with 30 subjects receiving one form of visual discrimination training therapy, while the other 30 will receive another form of visual discrimination training.

2. Gender and age range: Subject gender is intended to have an even distribution. Women and men are both susceptible to the conditions that would qualify participation as study subjects in the proposed research. All subjects who have sustained vision losses as a result of brain damage, that are able to give informed consent and are willing and able to undergo testing and training will be eligible for inclusion in this study, subject to the limitations described in the following paragraph. Since vision losses as a result of brain damage do occur in women, we will aim to recruit equal numbers of men and women in the proposed study.

Since the goals of the proposed research are to examine the effects of visual retraining on visual performance following adult-onset visual cortical damage, children will not be recruited as subjects. Only adults ranging in age between 21 and 75 years of age will be recruited. The upper limit of 75 years of age is included to ensure that subjects are able to properly fixate during the course of training. Children under the age of 21 will be excluded from enrollment as they rarely develop brain injury affecting the visual system. Very young children (<10 years of age) may also not be able to understand the study components/requirements or maintain the discipline necessary to participate correctly in daily visual training. Moreover, on the rare occasion that children develop V1 damage, because their brain is more plastic than that of adults, and because long range connections are still forming in their visual system, they are sometimes able to recover from their hemianopic deficit (see work by Tinelli et al., 2013). This may occur because after such damage, children can more easily develop abnormal connectivity between visual areas within and between their two brain hemispheres (Bridge et al., 2008), endowing their residual vision with properties that are not seen in subjects who sustain V1 damage in adulthood. As such, children do not form a suitable population for the proposed study. Finally, teenagers and younger children have not been subjects in our preliminary studies, so it is unknown whether their perceptual learning after cortical damage is comparable to that in adults. Whether and what kind of visual retraining may be beneficial to children and teenagers requires completely separate and novel scientific investigations, which are outside the scope of the proposed application.

References

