Eye examination: A complete medical history, eye history, and eye examination will be performed in order to determine eligibility for the study. A comprehensive, routine dilated eye exam that includes slit lamp examination and retinal optical coherence tomography (OCT), will be performed on each patient by a qualified ophthalmologist or neuro-ophthalmologist at each site to verify ocular health. OCT should have a signal strength of at least 6, otherwise the test should be repeated. If any problems or signs of ongoing, developing or progressing eye disease are observed, this will constitute grounds for exclusion from the study. The eye examination will include Snellen best corrected acuity, intraocular pressure measurement, exophthalmometry, motility, external examination, slit lamp examination, dilated fundus examination and OCT imaging of the retina.

Visual field testing: Certified technicians will perform 24-2 Humphrey visual fields on each subject. Fixation and pupil monitoring will be “on” for each test. The examination will be performed twice with a 30-minute rest period after each test. Examinations need to be done twice at baseline, with the second test used for future analysis, to ensure that patients are proficient in performing the tests at baseline, so that we can rule out practice on the test as a reason for post-training improvements. During Humphrey perimetry, the eye tracker will be engaged at all times. Tests will be repeated if the patient fails to generate acceptable test reliability (in terms of rate of fixation breaks, false positives and false negatives). If repeated perimetry tests fail to yield acceptable reliability measures (as per device specifications), this will constitute grounds for excluding the subject from the study. Our research to date shows that accurate fixation is critical both to generate reliable perimetry results (our primary outcome measure) and to elicit training-induced improvements in the blind field. All excluded subjects will be replaced with a new enrollment.

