computerized tests developed at the University of Rochester. These tests present visual stimuli consisting of drifting random dots. The subject is required to indicate (by pressing the corresponding keys on the computer's keyboard) the global direction of motion in the stimulus. While simple visual perception can be assessed during routine visual testing in the clinic, complex aspects of visual processing cannot. This is a significant shortcoming of the field right now and one that we will address in the present study. When sequentially measuring global direction discrimination performance at different locations across the intact field, and into the blind field, the blind field location where the patient's direction discrimination performance falls to chance (~50% correct) in a 100 trial block will be designated as the first training location. The potential subject will sit comfortably and be instructed on how to correctly position him/her self in the head/chin rest. The subject's laptop computer (or one provided for the subject) will be set up in front of the subject. After an explanation by the technician, eye movement fixation monitor will be adjusted. A full explanation of the task, including need for steady fixation, response to fixation "catch trials", alternative test stimuli and appropriate responses will be given. The subject will then be asked to perform both training tasks at fixation and then at peripheral locations in their blind field selected for training based on the Humphrey visual field test results. Feedback will be provided by the technician during training until independence is achieved.

The National Eye Institute Visual Functioning Questionnaire – 25 (VFQ-25) version 2000: This questionnaire will be completed online in the self-administered format by the subject, in the presence of qualified site personnel. The subject may ask for assistance from site personnel as needed. A fully validated neuro-ophthalmologic disease supplement of 10 items, also on line, will be used in addition to the standard VFQ-25.

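### The Purpose asks whether training reduces visual defects, but all subjects are randomised between two trainings with no designated control and no stated between-cohort test, so randomisation does not identify that effect

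*Combined protocol and SAP*

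**What the plan says.** - **Question.** The Purpose section says: "This research is designed to determine if different visual training treatments are capable of reducing visual defects". The same section speaks of quantifying the effect of training.
- **Arms.** The Background describes "randomizing them to one of two treatment groups, training them with one of two types of visual discrimination training therapy". Under Number of subjects the split is given as "with 30 subjects receiving one form of visual discrimination training therapy, while the other 30 will receive another form of visual discrimination training". No sham, untrained, waiting-list or delayed-start group is described. The section on racial and ethnic distribution mentions control subjects in passing, but no control group is defined anywhere.
- **Where training takes place.** The Background refers in general to "visual restitution training using visual discrimination tasks presented in the blind field". For the first training location, the Baseline Visit section says "the blind field location where the patient's direction discrimination performance falls to chance (~50% correct) in a 100 trial block will be designated". At that visit subjects "perform both training tasks at fixation and then at peripheral locations in their blind field selected for training". Under Randomization, treatment locations as well as cohort are pre-assigned by subject ID. Neither training form is defined by arm.
- **Analysis.** Data analysis and data monitoring maps change in the Humphrey fields over time and quantifies the area that gains or loses more than 6 dB. Regression and ANOVA then relate change to subject age, lesion age, deficit size and type of neurologic event. Training cohort is not listed and no between-cohort test is stated.
- **Safeguards.** The injury must be at least 90 days old, with a stable defect on at least two reliable fields. Unreliable fields (more than 20% fixation losses, false positives or false negatives) exclude a subject. The eye tracker is engaged throughout Humphrey perimetry. The Humphrey test is done twice at baseline and the second is analysed, "so that we can rule out practice on the test as a reason for post-training improvements". MAIA fixation is measured at the Baseline Visit and again at Visit 3.

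**The concern.** Two equally effective trainings and two equally inert ones give the same randomised result: no difference between cohorts. The question in the Purpose would then be answered from before-after change, which has no concurrent comparison. The stated analysis leads there in any case, because it describes change over time and leaves cohort out.

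The Background faults earlier studies for lacking randomisation and blinding, and says the results will go to the FDA for approval. Randomising between two trainings protects the comparison of those trainings. It gives no protection to a claim based on improvement from baseline in both of them.

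**Working it through.** **1. Sample size.** Under Number of subjects: "20 subjects will be recruited at each of three study sites, leading to a total of 60 subjects". 3 × 20 = 60 and 30 + 30 = 60, so the counts agree. No effect size, SD, power or primary-test alpha is given, so 60 cannot be derived from a power formula.

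**2. What each comparison can identify.** Write the mean change in cohort A as T_A + S and in cohort B as T_B + S. T is the effect of that training. S is everything common to both cohorts: practice, fixation, regression to the mean and drift.
- Between cohorts: (T_A + S) − (T_B + S) = T_A − T_B. S cancels, and a relative effect remains.
- Before-after: T_A + S and T_B + S. S stays in.

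The Purpose asks about T_A and T_B. Randomisation delivers only T_A − T_B, which equals an absolute effect only if one arm is known to be inert.

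**3. How far the safeguards reach.**
- Practice: the second baseline field follows the first after a 30-minute rest. It deals with first-test learning on that day. It does not cover later learning up to the pair of fields at Visit 4 (week 29).
- Fixation: the plan calls accurate fixation critical to reliable perimetry. Tracking monitors fixation but does not make it equal before and after. MAIA is repeated, but the analysis section does not use it.
- Drift: the Background puts spontaneous recovery in the first 2-3 months and says stability afterwards is believed. The 90-day minimum lies at the end of that window.
- Regression to the mean: entry requires locations below 15 dB, and no step separates the selecting field from the baseline field.

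**4. Size for a before-after test (assumed shifts).** One-sample t-test on change, two-sided 0.05, true training effect zero, S expressed in SDs of change:

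| S (SD) | n = 30 | n = 60 |
|---|---|---|
| 0 | 5% | 5% |
| 0.1 | 8% | 12% |
| 0.2 | 19% | 33% |
| 0.3 | 36% | 63% |
| 0.5 | 75% | 97% |

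A between-cohort test stays at 5% throughout if S is equal in both cohorts.

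**5. Size on the plan's 6 dB threshold (assumed values).** Let a location's test-retest difference be normal with SD 3 to 6 dB and mean shift m. Then P(gain > 6) = P(Z > (6 − m)/SD) and P(loss > 6) = P(Z > (6 + m)/SD).

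| m (dB) | SD 3: gain / loss | SD 6: gain / loss |
|---|---|---|
| 0 | 2.3% / 2.3% | 15.9% / 15.9% |
| 0.5 | 3.3% / 1.5% | 18.0% / 13.9% |
| 1 | 4.8% / 1.0% | 20.2% / 12.2% |
| 2 | 9.1% / 0.4% | 25.3% / 9.1% |

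With no shift, gains and losses balance, so noise alone does not imitate restoration when both are reported. At 1 dB, gains rise by 2.5 to 4.4 locations per 100.

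**6. What the between-cohort test can detect.** With 30 per cohort, two-sided 0.05 and 80% power: (1.960 + 0.842) × √(2/30) = 0.72 SD (0.74 SD by the t-distribution). At a true difference of 0.5 SD, power is about 48-49%.

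**The case against.** The best defence is that the gap named in the Background is missing randomisation and blinding, and that two masked trainings close it. A between-cohort comparison cancels practice and drift common to both cohorts. The safeguards are real: time since injury, stable and reliable fields, demonstrated fixation, eye tracking, and a repeat baseline field. All of this stands, but it supports a relative question, and the plan does not state the comparison that would use it.

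Three stronger readings are tempting and should not be adopted.
- *Both cohorts certainly receive active blind-field training.* This is the natural reading of the Background and the Baseline Visit section, but it is not stated by arm. Treatment locations are pre-assigned along with cohort, so location may differ between cohorts and one may be an undeclared control. The supportable point is that the arms are undefined.
- *The design can tell nothing about practice, fixation or drift.* The safeguards reduce each of these. What is missing is separation by randomisation.
- *Training amounts to months of rehearsing perimetry.* The task described is direction discrimination of moving dots. Training is called daily, but its duration is not stated; week 28 is a visit date. The plan ties fixation to perimetric reliability and does not say that better fixation raises sensitivity.

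The trained-minus-untrained contrast proposed below has a weakness too. The Background expects training to improve untrained aspects of vision, which would shrink the contrast.

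**Conclusion.** The concern holds in this form. The Purpose asks about an absolute effect, the randomisation supports at most a relative one, and the stated analysis makes neither comparison between cohorts. Equal improvement in both cohorts would be open to several explanations that the safeguards reduce but do not exclude. The claim that a second field at the same visit rules out practice is too strong.

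The structural point needs no assumed number. Its size does: the 8% to 97% range rests on assumed shifts of 0.1 to 0.5 SD, and the decibel figures on assumed SDs and shifts. These are illustrations, not estimates for this trial. If the sponsor states that one arm is a control, a between-cohort difference could answer the Purpose, provided that the control is inert for the measured outcome and the comparison is pre-specified. The change should be made; it does not require an added arm.

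**What to change.** 1. **Analysis and arms.** In Data analysis and data monitoring, make the between-cohort comparison of perimetric change, adjusted for baseline, the primary analysis. State each arm's task and field location, and whether one arm is the control. If neither is, reword the Purpose and Background to ask whether one training reduces the deficit more than the other, and say that before-after change in both cohorts will not by itself be reported as an effect of training.
2. **Supporting contrast.** From the 24-2 fields already collected, report for each subject the change at trained blind-field locations minus the change at distant untrained locations. Choose the reference locations according to each cohort's assigned training location. State that the contrast is conservative if training spreads.
3. **Practice and fixation.** In the Screening Visit text on visual field testing, say that the repeat field reduces practice effects instead of ruling them out. Report change in MAIA fixation from the Baseline Visit to Visit 3 beside the perimetric change.

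Cost: protocol wording and a little more analysis, with no new subjects or tests. The downside is a narrower claim, with 80% power only for between-cohort differences of about 0.72 to 0.74 SD.

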6. At least two reliable HVF's demonstrating good fixation and a stable homonymous incomplete (e.g., quadrantanopia or relative defect) or complete hemianopia
7. Reliable HVFs with repeat HVFs if randomization takes place more than 4 weeks after screening visit
8. A homonymous, contiguous visual deficit measured by the 24-2 HVF to be a minimum of two testing locations high and two testing locations wide, where impaired locations are any that measure a threshold of less than 15 dB
9. Demonstration of good fixation on visual training task – able to fixate the small targets presented as fixation letters reliably for 1000ms with jitter over less than 1 degree of visual angle in any direction away from target edge

Exclusion Criteria at Screening Visit

1. Physical, neurological or mental disability that would interfere with study intervention
2. Concurrent participation in "vision therapy" other than standard occupational or physical therapy
3. Unreliable visual fields on prior testing, indicated by greater than 20% fixation losses, false positives, or false negatives.
4. Inability to discontinue medications judged to affect training and/or assessment (e.g., Ritalin, amphetamines, dopamines, or chemotherapeutic agents)

5. Physical condition likely to preclude completion of the clinical trial (e.g. end-stage or uncontrolled cancer, uncontrolled epilepsy, or end-stage heart disease)
6. Ocular or neurological condition that would interfere with training or assessment (e.g. damage to the optic nerves or lateral geniculate nucleus, any degenerative ocular condition)
7. Best corrected vision worse than 20/40 in either eye
8. Impaired foveal Humphrey sensitivity as indicated by the HVF tests.
9. Presence of vision loss resulting from ocular disease or disorder
10. Presence of bilateral visual acuity loss from any source

Additional Exclusion Criteria at Randomization Visit

1. Inability to demonstrate fixation stability on eye movement monitored testing
2. Inability to follow training instructions

Concomitant Medications

1. No medication is required for participation in the study
2. Allowed Concomitant Medications: Any medications that do not affect learning or motor performance are allowed. All concomitant medications must be used according to the prescriber's instructions.
3. Disallowed Medications: Ritalin, amphetamines, dopamines, or chemotherapeutic agents are specifically disallowed. Other medications may be disallowed based upon subject's individual side-effects (e.g. severe drowsiness, tardive dyskinesia, etc.). The site PI should contact the enrollment center to discuss findings and appropriate action in the event use of any disallowed medication is discovered. In all cases, the use of any disallowed medication should be documented along with any applicable instructions to the subject.

Discussion of Eligibility Criteria

Adults were chosen because the incidence of stroke-induced hemianopia is most frequent in adults, and because reliability and persistence are required for following the training regime. Older adults (65-75 years) were not excluded as they performed equally well in pilot perceptual training compared to younger adults. However, adults older than 75 years old are excluded from enrollment because they present with a greater incidence of ocular, physical, and/or mental conditions that can interfere with their ability to train effectively. In addition, our preliminary studies over the last 10 years show that hemianopic subjects older than 75 years have increased problems with concentration and maintaining steady fixation, both of which are absolutely necessary for successful training in the present trial.

Methods and procedures

1 - Screening Visit (Visit SC)

Informed consent: At the screening visit, a signed informed consent document will be completed. This consent form describes the interventions and enumerates the risks and benefits of participation. It will include consent for screening evaluation as well as consent for randomization if subject is found to be eligible. Potential subjects will have the opportunity to ask questions and receive answers prior to signing the consent.

Eye examination: A complete medical history, eye history, and eye examination will be performed in order to determine eligibility for the study. A comprehensive, routine dilated eye exam that includes slit lamp examination and retinal optical coherence tomography (OCT), will be performed on each patient by a qualified ophthalmologist or neuro-ophthalmologist at each site to verify ocular health. OCT should have a signal strength of at least 6, otherwise the test should be repeated. If any problems or signs of ongoing, developing or progressing eye disease are observed, this will constitute grounds for exclusion from the study. The eye examination will include Snellen best corrected acuity, intraocular pressure measurement, exophthalmometry, motility, external examination, slit lamp examination, dilated fundus examination and OCT imaging of the retina.

Visual field testing: Certified technicians will perform 24-2 Humphrey visual fields on each subject. Fixation and pupil monitoring will be “on” for each test. The examination will be performed twice with a 30-minute rest period after each test. Examinations need to be done twice at baseline, with the second test used for future analysis, to ensure that patients are proficient in performing the tests at baseline, so that we can rule out practice on the test as a reason for post-training improvements. During Humphrey perimetry, the eye tracker will be engaged at all times. Tests will be repeated if the patient fails to generate acceptable test reliability (in terms of rate of fixation breaks, false positives and false negatives). If repeated perimetry tests fail to yield acceptable reliability measures (as per device specifications), this will constitute grounds for excluding the subject from the study. Our research to date shows that accurate fixation is critical both to generate reliable perimetry results (our primary outcome measure) and to elicit training-induced improvements in the blind field. All excluded subjects will be replaced with a new enrollment.

Determination of eligibility: Sites having potential subjects for inclusion into the study will collect the required documentation at the Screening visit and forward relevant medical history, two sets of Visual Fields and an MRI or CT scan of the brain. The medical history will be sent to the Principal Study PI who will, jointly with the Site PIs, review the records for eligibility criteria. The visual fields will be sent to the Visual Field Reading Center for confirmation of visual field defect and reliability/stability of testing. The reading center will forward its information to the Principal Study PI who will jointly determine with the Site PIs whether the subject should appear for a Baseline Visit.

2 - Baseline Visit (Visit BL; 2-4 weeks post SC)

Eye examination: The history and eye examination as described in Visit SC will only be repeated if more than four weeks has elapsed between the Visit SC and Visit BL.

Visual field testing: Humphrey visual field testing as described above will only be repeated if more than four weeks has elapsed between Visit SC and Visit BL.

Eye fixation testing and restoration protocol training: Each subject will undergo MAIA perimetry in order to assess fixation quality and patterns. MAIA testing is a fundus-controlled form of perimetry, and as such, is the most precise way of performing gaze-contingent stimulus presentation. The test output includes a detailed mapping of each patient’s fixation locations during stimulus presentation, allowing us to quantify the spread of their eye movements around the fixation spot.

In addition to performing the MAIA, we will assess the ability to visually process complex visual stimuli in the normal and abnormal portions of the visual field in each subject, using

computerized tests developed at the University of Rochester. These tests present visual stimuli consisting of drifting random dots. The subject is required to indicate (by pressing the corresponding keys on the computer's keyboard) the global direction of motion in the stimulus. While simple visual perception can be assessed during routine visual testing in the clinic, complex aspects of visual processing cannot. This is a significant shortcoming of the field right now and one that we will address in the present study. When sequentially measuring global direction discrimination performance at different locations across the intact field, and into the blind field, the blind field location where the patient's direction discrimination performance falls to chance (~50% correct) in a 100 trial block will be designated as the first training location. The potential subject will sit comfortably and be instructed on how to correctly position him/her self in the head/chin rest. The subject's laptop computer (or one provided for the subject) will be set up in front of the subject. After an explanation by the technician, eye movement fixation monitor will be adjusted. A full explanation of the task, including need for steady fixation, response to fixation "catch trials", alternative test stimuli and appropriate responses will be given. The subject will then be asked to perform both training tasks at fixation and then at peripheral locations in their blind field selected for training based on the Humphrey visual field test results. Feedback will be provided by the technician during training until independence is achieved.

The National Eye Institute Visual Functioning Questionnaire – 25 (VFQ-25) version 2000: This questionnaire will be completed online in the self-administered format by the subject, in the presence of qualified site personnel. The subject may ask for assistance from site personnel as needed. A fully validated neuro-ophthalmologic disease supplement of 10 items, also on line, will be used in addition to the standard VFQ-25.

Randomization: Eligible subjects will receive their randomization assignment. All subjects will be double masked. Treatment locations and training cohort will be pre-assigned for all subject ID numbers and given to each subject at the end of visit BL. The site will then call the DCBC to obtain the subject ID to be used for each randomized subject and enter this number into the training software, which includes the randomized stimulus sequence.

3 – Post training visit (28 week visit +/- 2 weeks)

Eye fixation testing and restoration protocol testing: The eye fixation testing and protocol testing will be repeated as described for visit BL.

The National Eye Institute Visual Functioning Questionnaire – 25 (VFQ-25) version 2000 and supplement will be repeated, as described for Visit BL.

4 – Post training clinic visit (29 week visit +/-2 weeks)

Eye examination: The history and eye examination will be repeated as described for Visit SC.

Visual field testing: Visual field testing will be repeated as described for Visit SC.

Assessment Schedule

Visit Number	1 (screening)	2 (2-4 weeks post screening)	3 (28 weeks +/- 2 weeks)	4 (29 weeks +/- 2 weeks)
Informed Consent	Y			
Inclusion/Exclusion Criteria	Y			
Demographics	Y			
Medical History	X			X
Concomitant Medications	X			X
Slit-lamp exam	X			X
Retinal Optical Coherence Tomography	X			X
24-2 Humphrey	X			X
24-2 Humphrey repeated	X			X
MRI/CT	Z			
Comprehensive routine dilated eye exam*	X			X
Visual Functioning Questionnaire		Y	Y	
VFQ supplement		Y	Y	
MAIA perimetry		Y	Y	
Eye fixation testing and restoration protocol		Y	Y	

X Performed by clinician

Y Performed by study personnel

Z From patient chart

*dilated fundus exam, Snellen best corrected acuity, intraocular pressure, exophthalmometry, motility, external exam

Unscheduled telephone contacts: These contacts may be initiated by the sites in response to contact from the TC indicating compliance (e.g. missed training sessions) or performance issues (e.g. fixation losses). These contacts may be initiated by the subject for any reason, including equipment failure, motivational issues, or notification of inter-current events that may affect training. The date and reason for the unscheduled telephone contact will be recorded in the source documentation.

Unscheduled visits: These visits may be initiated by the sites in response to contact from the TC indicating compliance (e.g. missed training sessions) or performance issues (e.g. fixation losses).

These visits may be initiated by the subject for any reason, including equipment failure, motivational issues, or notification of inter-current events that may affect training. The date and reason for the unscheduled visit will be recorded in the source documentation, along with whatever portions of the visit protocol were conducted.

Premature withdrawal: Subjects have the right to withdraw from the study at any time without prejudice. The Site Investigator may withdraw training from a subject in the study in the event of inter-current illness, adverse events, or other reasons concerning the health or well-being of the subject, or in the case of lack of cooperation, non-compliance, protocol violation or other administrative reasons. In the event of premature withdrawal from the study, the Premature Withdrawal (PW) Visit procedures and evaluations should be completed whether or not the withdrawal is determined at a regularly scheduled study visit or at an unscheduled visit. In instances where the subject refuses to return for a PW visit, the Steering Committee may recommend an attempt to obtain outcome data by a visit to a non-participating ophthalmologist. Reasons for withdrawal of the subject prior to completion of the study must be stated in the case report form and in the site source documentation for all study subjects who were enrolled in the study. The DCBC must be informed within 24 hours of all study subjects who are withdrawn due to an adverse event.

Early Discontinuation of Study Training: In the instance that subjects refuse to continue specified training but choose to remain in the study, then scheduled visits should be designated as a NOTRAIN visit and all regular visit activities will be completed.

Re-Entry Visits: In the instance that subjects who opted for Early Discontinuation of Study Training or Premature withdrawal decide to re-enter the study, then a Re-Entry visit with a protocol identical to a Baseline Visit (BV) will be performed, except that the subject's original randomization schedule will be utilized.

Adverse events: An adverse event is any symptom, sign, illness, or experience which develops or worsens during the course of the study, whether or not the event is considered related to the study intervention. A serious adverse event is defined as any adverse medical experience that results in any of the following outcomes:

- death;
- is life-threatening;
- requires inpatient hospitalization or prolongation of existing hospitalization;
- is a congenital anomaly/birth defect; or
- requires medical or surgical intervention to prevent permanent impairment or damage.

At each subject visit the site study staff will assess adverse events by recording all voluntary complaints of the subject and by assessment of clinical and laboratory features. At each study visit, the subject should be questioned directly regarding the occurrence of any adverse experience since his/her last visit.

All adverse events, whether observed by the Investigator, elicited from or volunteered by the subject, should be documented. Each adverse event will include a brief description of the experience, the date of onset, the date of resolution, the duration and type of experience, the

severity, the relationship to investigational product, contributing factors, and any action taken with respect to the study device. All adverse events occurring between the time of consenting and subject completion or withdrawal from the study will be recorded. Follow up will continue until the adverse event is resolved, including those unresolved at the time of subject concluding study participation.

Data analysis and data monitoring: HVF test results will be analyzed using a custom program in Matlab. Changes in HVF over time will be mapped across the visual field and the area of the visual field that increases or decreases in sensitivity by >6dB will be quantified. Subject age, lesion age, visual deficit size, and type of precipitating neurologic event will be analyzed using linear regression and ANOVA to determine if any of these factors are correlated with change; when appropriate, post-hoc analyses will be conducted using Tukey's HSD and a family-wise Type I error rate of 0.05.

Data storage and confidentiality

- a. Data will be stored on a secure, encrypted server hosted on the URMC private network. Only study personnel directly involved in raw data processing and analysis will have access to data files containing protected health information.
- b. A separate key will be created linking the subject identifiers with a unique study ID number to avoid any direct identifiers stored with the collected data.
- c. Data collected will be used for future research studies.

Risks/benefit assessment

- a. Risk Category: Minimal risk
